The CTI aims to improve *patient activation*, which is measured as having the skills, knowledge, and motivation to participate as effective members of the care team.⁶⁷ We will use the Wallston Perceived Health Competency Scale.

Upon study exit, we will measure our *primary outcome, health care use* within 30 days of ED discharge, through survey and administrative data from both local health systems and the insurers. We will also measure the costs of health care as well as the CTI program.

We will check the Social Security Death Index for death within 30 days for all subjects.

If a subject *withdraws* during follow-up, we will clarify the level of withdrawal that the subject is requesting—cessation of subject contact or removal from the study. If the subject requests cessation of contact, we will continue to review the subject's medical record to obtain health care use (e.g., ED use) outcomes. If a subject is *admitted to a skilled nursing facility*, which occurs in less than 2% of ED patients discharged home, we will track that outcome and measure those costs, but we will not survey those subjects.

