3.3. RATIONALE FOR INTERVENTION

We will implement and test the CTI for the intervention group because of its demonstrated effectiveness and cost-effectiveness, its applicability to the ED patient discharged home, its efficiency, particularly relating to activities in the ED, and its widespread use. We have chosen to use community-based

paramedics as the coaches for the CTI because these individuals are highly trained, available in all communities, and are highly respected by patients. Thus, paramedics are able to perform these visits in follow up to ED visits rapidly. Given that the CTI program has been tested using lay people, trained paramedics should be able to perform the required duties.

Table 2: Measures

	Measures	Time	Source/Approach
1. Demo -	Patient age, gender, marital status, race, ethnicity, education level, primary language, home ownership, living status, home address	ED	Patient survey
	Patient relationship with PCP	ED	Patient survey
	Insurance plan / number	ED	Epic review
	Primary Care Medical Home certification level	ED	Health systems
2. Clinical	New home services (since ED visit)	Day 30	Patient survey
	ED medications prior to assessment, chief complaint, final diagnosis (ICD-10), discharge medications, and instructions	ED	Epic review
	CTI Coaching & Services Forms* Personal Health Record (PHR) Home Visit/PHR Discussion Checklist Follow-up Phone Calls Checklist Patient Activation Assessment Medication Discrepancy Tool Care Transitions Measure - 3	CTI Coach home visit & coach follow up calls	CTI program records
3. Covariates	Medical history, including Charlson Comorbidity Index	ED	Patient survey
	Healthcare: Medications, home services, ED / hospital use	ED	Patient survey/ Epic review
	Health Status: Short Form-12 ⁶⁸	ED	Patient survey
	Disability Status: ADL ⁶⁹	ED	Patient survey
	Cognition: Short Blessed Test (BOMC)	ED	Patient survey
	Social Isolation: PROMIS Social isolation short form	ED	Patient survey
	Depression: PHQ-9	ED	Patient survey
	Anxiety: GAD-2	ED	Patient survey
Health literacy	ED	Patient survey	
4. Outcomes			
	Family Caregiver Activation in Transitions	ED, Day 30	Caregiver survey
	Understanding of red flags	Day 4	Patient survey
	Medication changes implemented	Day 4	Patient survey
	Follow up with PCP, specialists, urgent care	Day 4, 30	Patient survey / Epic review
	Wallston's Perceived Health Competency Scale (PHCS)	ED, Day, 30	Patient survey, Caregiver survey

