6.3. RESEARCH PROCESSES

The informed consent, baseline survey and randomization will be completed in the ED by the study RA. To facilitate scheduling the coach home visits the RA will know the coach's weekly availability. For those subjects randomized to the intervention group, the RA will schedule the coach home visit within 24 hours of ED discharge ideally and then send the paramedic coach the appointment time, patient's contact information and ED discharge summary via email. To ensure that all PHI is communicated securely, UW coaches will be provided with UW Department of Medicine email addresses and at UR the coaches will also be provided with UR email addresses. Thus, all communication will be within each institution's secure, HIPAA compliant email system.

Blinded research staff will be responsible for all research surveys for the patient and caregiver. These are intended for all subjects (control and intervention group) and independent of the clinical CTI program delivered to the intervention group.

Patient subjects will be contacted four days after ED discharge. The RA will telephone the subject and complete a survey that evaluates the program fidelity and initial outcome measures (Table 2). We chose this time point because patients should have made medication changes (e.g., started an antibiotic) and contacted their provider for follow up by then. We anticipate that the survey will take no longer than 10 minutes to complete.

Patient subjects will be re-contacted thirty days after ED discharge. The RA will re-contact all subjects and complete a final survey. We anticipate that the survey will take no longer than 10 minutes to complete the telephone survey. The RA will inform subjects of the research phone numbers from which all calls will be made. It is anticipated that providing this information will re-assure subjects and give an increase sense of comfort knowing who is calling them.

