If, at the time the follow-up assessments are due (Day 4 and Day 30) the patient subject is either in the ED or inpatient in the hospital, research staff will go to the ED or inpatient hospital floor and request permission from the attending health care provider to visit the patient to complete the followup survey. If the provider states the research visit is inappropriate the RA will leave the ED/inpatient area immediately. The patient subject can decline the RA visit and study survey at any time. This change in data collection does not apply to the Caregiver subject.

Caregiver subjects will be re-contacted thirty days after ED discharge. The RA will re-contact all subjects and complete a final survey. We anticipate that the survey will take no longer than 10 minutes to complete the telephone survey. The RA will inform subjects of the research phone numbers from which all calls will be made. It is anticipated that providing this information will re-assure subjects and give an increase sense of comfort knowing the who is calling them.

The RA will conduct a medical record review at the end of the study. We have built a lag time because we recognize that it can take months for the medical record to be fully updated with care episodes, discharge diagnoses, etc. The collected data are represented in Table 2.

Records Management: All data will be maintained initially on paper and then entered in REDCap, an electronic data management system on a secure server maintained by the UW Department of Medicine. The PI and coordinator are responsible for monitoring data quality in conjunction with the study team. Reports will be generated and reviewed regularly to show the status of all subjects and bring forward any problems with study processes and data completeness.

Individuals who decline to participate will not have any identifiable information retained. We will retain the following variables to compare those participating to those who decline to participate: 1) age up to 89 years and age range for subjects ≥ 90 years, 2) sex, 3) race, 4) chief complaint, 5) reason for declining study participation.

All documentation will be stored in the UW or UR Department of Emergency Medicine locked office space. No later than the end of the study, the forms will be scanned and stored on secured network drives at UW and the paper copies will be destroyed.

Table 3: Schedule of Activities

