Missing Data: Inference based on the proposed method is valid provided that missing data follows the missing completely at random (MCAR) assumption. However, the occurrence of missing data may depend on the observed response and such as missing at random (MAR) mechanism will generally bias the estimates. Sensitivity analysis will be performed to examine the MCAR assumption. If it is deemed to be severely violated, we will report treatment effects using weighted GEE that addresses the MAR mechanism.^{74,75} Biased estimates may arise if missing data does not follow the MAR mechanism, or non-ignorable non-response (NINR). Although unanticipated in this study, we will examine this potential NINR using the mixture model approach.⁷⁶

Future Planned Analysis: We are requesting to retain the data in an identified form for 10 years after completion of this study for future analyses of health care utilization and claims data from subjects' health insurance providers so as to understand if a paramedic coach reduces health care use and costs. We will keep the deidentified data indefinitely.

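### Subjects admitted to a skilled nursing facility are excluded from the follow-up surveys by rule, which creates small but avoidable outcome-dependent missing data, mainly in the day-30 survey measures

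*Combined protocol and SAP*

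**What the plan says.** Section 3.2 (Rationale for study design and measures) deals with admission to a skilled nursing facility during follow-up, an event "which occurs in less than 2% of ED patients discharged home". For these subjects, "we will track that outcome and measure those costs, but we will not survey those subjects". No reason for the survey exclusion is given. As worded, the rule has no time limit.

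Section 6.3 (Research processes) states the general day-30 procedure without an exception for facilities: "The RA will re-contact all subjects and complete a final survey". For subjects who are in an ED or are inpatients when the day-4 or day-30 survey is due, "research staff will go to the ED or inpatient hospital floor and request permission from the attending health care provider to visit the patient" and complete the same survey there.

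Table 2 shows which outcomes depend on the survey. "Understanding of red flags" and "Medication changes implemented" (Hypotheses 1A and 1B) come from the day-4 patient survey alone. The Wallston Perceived Health Competency Scale, which section 12.2 compares between arms for Hypothesis 2A, comes from surveys. Health-care use within 30 days comes from the patient survey and Epic review, and section 3.2 also names administrative data from the local health systems and insurers.

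The missing-data text in section 12.2 starts from missing completely at random and moves to weighted GEE if that is badly violated. On non-ignorable non-response (NINR) it says: "Although unanticipated in this study, we will examine this potential NINR using the mixture model approach". It has no rule for facility admissions.

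**The concern.** Section 2.2 lists nursing home placement among the poor outcomes of older ED patients. Facility admission happens after randomisation, and the intervention could plausibly affect it. A rule that stops the survey on admission therefore removes subjects from the survey endpoints because they did badly. If the arms differ in admission rate, or in how badly admitted subjects would have scored, the surveyed groups are no longer the randomised groups. The arm with more admissions then looks better on the survey measures than it should.

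Ordinary attrition has to be accepted, but this loss is chosen. The protocol already makes a greater effort for a comparable situation, a bedside visit to an acutely ill inpatient, yet does not allow a telephone call to a facility resident. Section 4.3 deliberately keeps subjects with sensory or cognitive limits, so expected difficulty in answering does not explain the difference.

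A second, smaller loss concerns ED visits outside the two health systems. The survey is one of the ways these are found (Appendix A, section 1.2), and for facility residents that route is closed.

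**Working it through.** **Inputs from the documents.** 2400 subjects, 1200 per arm, and 25% attrition (section 12.1); facility admission below 2% (section 3.2, with no source, time window or rate by arm); about 30% of participants with a caregiver present (section 12.2). The 2% figure has no derivation to reproduce.

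**Counts.**
- Ceiling on subjects excluded by the rule: 0.02 × 2400 = 48, or 24 per arm at equal rates.
- Planned attrition: 0.25 × 2400 = 600. The rule accounts for at most 48/600 = 8% of that number.
- Excluded subjects likely to have a caregiver, if the 30% applies to them: 0.30 × 48 ≈ 14.

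**Bias in a survey mean difference.** Let f be the share of an arm admitted to a facility, and D the shortfall of admitted subjects in SD units, taken as equal in both arms. Leaving them out raises that arm's mean by f × D, so the bias in the between-arm difference has size |f_control − f_intervention| × D. The day-30 analysis would have 1200 × 0.75 = 900 per arm. The standard error is √(2/900) = 0.047 SD, and the difference detectable with 80% power is 2.80 × 0.047 = 0.132 SD.

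The documents give neither admission rates by arm nor D, so the following are assumptions:

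| Rates in the two arms | D (SD) | Bias (SD) | In standard errors |
|---|---|---|---|
| 2% and 2% | any, equal | 0 | 0 |
| 2% and 1% | 0.5 to 1.5 | 0.005 to 0.015 | 0.11 to 0.32 |
| 2% and 0% | 0.5 to 1.5 | 0.01 to 0.03 | 0.21 to 0.64 |

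Rates of 3% and 1% with D = 1 also give 0.02 × 1 = 0.02 SD, but 3% exceeds the plan's own ceiling. The 2%-and-0% row gives the same contrast within it. Hypothesis 2A uses a rank test, so these mean shifts indicate scale only.

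**Binary measures (1A, 1B).** If other subjects succeed at rate b and admitted subjects are counted as failures, the shift is b × |f_control − f_intervention|. With 2% against 0% and b from 0.3 to 0.7, that is 0.6 to 1.4 percentage points. If admitted subjects instead succeed 40 points less often, it is 0.02 × 0.40 = 0.8 points. The standard error at b = 0.5 and 900 per arm is √(0.25 × 2/900) = 2.4 points. These figures are upper illustrations, because they treat every admission as occurring before the day-4 survey.

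**The texts side by side.** Section 3.2 excludes, section 6.3 includes everyone at day 30, and section 6.3 goes to the bedside for ED and hospital stays. Section 3.2 can be read as a specific exception to a general rule, but section 6.3 does not refer to it.

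**The case against.** The case for leaving the rule alone has several sound parts.

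- **Size.** Nothing in the documents suggests that admission rates differ by arm. With equal rates and equal shortfalls the bias is zero, and even the assumed extremes stay well inside one standard error. This stands.
- **Meaning of the endpoints.** The trial studies people living independently at home. Implementing one's own medication changes means something different when a facility gives the medication. This stands for 1B and calls for separate marking. It is weaker for the Wallston score and does not apply to health-care use.
- **Access.** The protocol describes no permission route into nursing facilities. That is true, but the route for hospital wards is an obvious model, and the survey is normally done by telephone.
- **A known cause.** Admission is recorded, so the missingness need not be non-ignorable, and section 12.2 says NINR will be examined. This stands as far as it goes. However, because no admitted subject is surveyed, the trial will hold no scores for such subjects, and any weighting or mixture model must rest on an assumption about them.

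A reader might infer three stronger things that the documents do not support:

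- **That the rule breaches intent-to-treat.** The statement in section 12.2 is about keeping subjects in their assigned group. Unsurveyed subjects stay in their group and in the study, with admission, costs, records and deaths still followed.
- **That their outside ED visits will be counted as none.** No text says so. Section 3.2 names insurer data, and Appendix A section 1.2 names caregiver as well as patient surveys. Such visits may be missed where those sources are lacking. That is possible, because Table 2 lists only survey and Epic for health-care use and section 12.2 places insurer claims under future analyses.
- **That all survey endpoints lose these subjects equally.** Someone admitted after day 4 was already due the day-4 survey, so 1A and 1B are affected only by earlier admissions.

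**Conclusion.** The concern holds as a small, avoidable weakness in data collection. Section 3.2 makes survey data missing because of a poor post-randomisation event, while section 6.3 makes the effort for comparable subjects in ED or hospital beds. The loss falls mainly on the day-30 Wallston score and on the survey's supplement on ED use outside the two systems, and on 1A and 1B only for admissions before day 4.

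At most about 48 of 2400 subjects are involved at the plan's 2% ceiling. The bias is zero if the arms are alike, and about 0.02 to 0.03 SD under assumed rates of 2% against 0% and a shortfall of 1 to 1.5 SD, against a detectable 0.132 SD. The rates by arm and the shortfall are assumptions.

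A reader might take this as a threat to the primary result. It is not, because repeat ED use is ascertained largely from records. The change is worth making because it is cheap.

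**What to change.** In section 3.2, delete the clause that excludes facility residents from the surveys. In its place:

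1. Attempt the scheduled call at the facility, with the facility's and the subject's agreement, on the model of the ED and inpatient visits in section 6.3. Ask at least the Wallston and health-care-use items.
2. If the subject cannot answer, take the health-care-use items from the enrolled caregiver, where there is one. Caregivers are already called at day 30, but on the plan's 30% assumption this covers only about 14 of 48 subjects.
3. Flag 1B responses where the facility administers the medication, and state in section 12.2 how flagged values enter the analysis.
4. Make sections 3.2 and 6.3 agree, and say what applies to a subject who has left the facility before a survey is due.
5. Report facility admissions by arm, so that readers can judge any remaining imbalance.

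The cost is a few dozen extra calls by existing research staff, a short protocol change, and some 1B values that need separate marking. No clinical procedure changes.

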3.3. RATIONALE FOR INTERVENTION

We will implement and test the CTI for the intervention group because of its demonstrated effectiveness and cost-effectiveness, its applicability to the ED patient discharged home, its efficiency, particularly relating to activities in the ED, and its widespread use. We have chosen to use community-based

paramedics as the coaches for the CTI because these individuals are highly trained, available in all communities, and are highly respected by patients. Thus, paramedics are able to perform these visits in follow up to ED visits rapidly. Given that the CTI program has been tested using lay people, trained paramedics should be able to perform the required duties.

Table 2: Measures

	Measures	Time	Source/Approach
1. Demo -	Patient age, gender, marital status, race, ethnicity, education level, primary language, home ownership, living status, home address	ED	Patient survey
	Patient relationship with PCP	ED	Patient survey
	Insurance plan / number	ED	Epic review
	Primary Care Medical Home certification level	ED	Health systems
2. Clinical	New home services (since ED visit)	Day 30	Patient survey
	ED medications prior to assessment, chief complaint, final diagnosis (ICD-10), discharge medications, and instructions	ED	Epic review
	CTI Coaching & Services Forms* Personal Health Record (PHR) Home Visit/PHR Discussion Checklist Follow-up Phone Calls Checklist Patient Activation Assessment Medication Discrepancy Tool Care Transitions Measure - 3	CTI Coach home visit & coach follow up calls	CTI program records
3. Covariates	Medical history, including Charlson Comorbidity Index	ED	Patient survey
	Healthcare: Medications, home services, ED / hospital use	ED	Patient survey/ Epic review
	Health Status: Short Form-12 ⁶⁸	ED	Patient survey
	Disability Status: ADL ⁶⁹	ED	Patient survey
	Cognition: Short Blessed Test (BOMC)	ED	Patient survey
	Social Isolation: PROMIS Social isolation short form	ED	Patient survey
	Depression: PHQ-9	ED	Patient survey
	Anxiety: GAD-2	ED	Patient survey
Health literacy	ED	Patient survey	
4. Outcomes			
	Family Caregiver Activation in Transitions	ED, Day 30	Caregiver survey
	Understanding of red flags	Day 4	Patient survey
	Medication changes implemented	Day 4	Patient survey
	Follow up with PCP, specialists, urgent care	Day 4, 30	Patient survey / Epic review
	Wallston's Perceived Health Competency Scale (PHCS)	ED, Day, 30	Patient survey, Caregiver survey
	Healthcare use within 30 days of discharge	Day 30	Patient survey / Epic review
	Death within 30 days of discharge (Social Security Death Index)	Day 30	Death Index
	Patient experiences of continuity	Day 30	Patient survey
	Cost of healthcare and CTI program	Day 30	Health systems, study
Program satisfaction	Day 30	Patient, caregiver survey	

*All forms copyrighted by [name]

4. CHARACTERISTICS OF THE RESEARCH POPULATION

4.1. SUBJECT CHARACTERISTICS

Number of Subjects: We propose to enroll 2400 ED patient subjects into the study, with 1200 of the enrollments coming at UW and 1200 at UR Medical Center-Strong Memorial Hospital or UR Medical Center-Highland Hospital. Of the 2400 subjects, 1200 will be randomized to the intervention group and 1200 to the control group. We will also enroll up to one informal caregiver per ED patient, resulting in up to 2400 additional subjects. Thus, the total number of subjects potentially enrolled in this study is 4800.

Gender and Age of Subjects: All patient subjects will be age 60 years and older, as this is a concern of the older adult population. Both men and women will be enrolled.

Informal caregiver subjects must be age 18 or older, and will be either male or female, depending on who is identified by the patient subject.

Racial and Ethnic Origin: Individuals of all races and ethnicities will be included.

Vulnerable Subjects: Older adults are the focus of this study as these problems are not as prevalent for younger individuals; thus evaluating transitional care for them is of likely little benefit and any developed knowledge may not be translatable to older adults. We will implement safeguards to protect this population:

1. The study staff will not be directly providing ED clinical care to the participants, thus eliminating any potential coercion.
2. Decisional capacity will be evaluated by the RA obtaining consent to ensure that participants understand the risk and benefits of the study before obtaining informed consent, unless the Health Care Power of Attorney has already been activated. The decisional capacity evaluation process that will be used has been approved by the UR IRB. It assesses the potential subject's understanding of the study. This process is more conservative than the UW IRB policy "Research with Adult Participants Lacking Capacity to Consent" (Section II) as all subjects will be tested in this minimal risk study. The PI ([name], emergency medicine), co-I ([name], geriatrician), and project director ([name], psychology degree, extensive community health/social work experience working with vulnerable populations) will ensure that all RAs who conduct the capacity assessment will be fully trained.
3. Informed consent to participate in the study will be obtained from patients. Patients without decisional capacity will be included if a caregiver with responsibility for the patient's health care consents to participation in the study. Priority of decision makers is as follows: 1) research power of attorney, if present; 2) court appointed guardian; 3) power of attorney for healthcare; 4) next of kin in the following order: spouse or registered domestic partner, adult child, parent, adult sibling, grandparent, adult grandchild, or close friend.
4. Informed consent will be obtained from the caregiver if present in the ED. The caregiver will be assessed for decisional capacity using the same methods as with the patient subject. Caregivers without decisional capacity will not be eligible to join study.

